#### 7. CONCOMITANT THERAPY

Concomitant medication data will not be collected or entered into the case report form except for concomitant hydroxyurea and intrathecal chemotherapy; however, the subject's medication record will contain a list of concomitant medications. All supportive measures consistent with optimal patient care should be provided throughout the study according to the departmental standards.

- **7.1. Allowed Concomitant Therapy:** Prophylactic or therapeutic intrathecal therapy is allowed, if central nervous system leukemia involvement is diagnosed after enrollment in this clinical trial. The use of hematopoietic growth factors or transfusions is allowed. The use of hydroxyurea is permitted at any time during the study period for cytoreduction. Corticosteroids (e.g. for management of allergic reactions, prophylaxis, etc.) are also allowed. Use of other immunosuppressive therapy, e.g. tacrolimus, may be allowed at the disgression of the clinical provider. Other supportive care studies are allowed, even if under an IND.
- **7.2. Prohibited Concomitant Therapy:** Patients may not receive other investigational anti-neoplastic therapy drugs, excluding therapy as described in previous Section "Allowed Concomitant Therapy". Patients may not receive radiotherapy during the study.

The following medications should be strictly prohibited during the study treatment period, unless there are no signs of QTc prolongation in scheduled EKG:

- Drugs with a known risk to induce Torsades de Pointes: All QT-prolonging drugs (see Table 1 in of Appendix 1) are prohibited for all patients until permanent discontinuation of study treatment.
- Drugs with a conditional risk to induce Torsades de Pointes: Any QT prolonging medication with
  a conditional risk of inducing Torsades de Pointes listed in Table 2 of Appendix 1 are prohibited
  for all patients from screening through permanent discontinuation of study treatment, except for
  the assumptions described in Section 6.1.7. for the treatment of diarrhea and nausea. These
  exceptions must be discussed in advance with the Sponsor on a case-by-case basis.
- Warfarin and Coumarin-type anticoagulants within 1 week prior first CB-103 dose.

Page | 29 04/25/2024

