#### 3. STUDY POPULATION

#### 3.1. Inclusion Criteria:

**3.1.1.** Adolescent (12 to 18 years) and adult (19 to 60 years) patients who have relapsed or refractory T-cell lymphoblastic leukemia (T-ALL) or T-Cell lymphoblastic lymphoma (T-LBL) according to 2017 WHO classification [29] and NCCN v1 2021 [30]:

Patients must have  $\geq 5\%$  blasts in the bone marrow as assessed by morphology on standard bone marrow biopsy and aspirate or less than 5% blasts in the bone marrow in presence of extramedullary relapse, excluding isolated central nervous system (CNS) relapse. However, if an adequate bone marrow sample cannot be obtained, patients may be enrolled if there is unequivocal evidence of leukemia with  $\geq 5\%$  blasts in the peripheral blood.

- **3.1.2.** Patients are eligible independently of Notch pathway activation in the leukemic blasts: however, a fresh marrow/blood sample must be obtained before starting the study treatment to classify the patients as being either Notch positive or negative.
- **3.1.3.** Leukemic blasts must express of at least 2 of the following immune phenotyping: CD1a, CD2, CD3, CD4, CD5, CD7, CD8, CD34, TCR $\alpha$ B, TCR $\gamma$ S, cyCD3
- **3.1.4.** Patients have adequate performance status (ECOG ≤2) for patients ≥16 years old, Lansky score >50 for patients <16 years old.
- **3.1.5.** Patients must be 12 to 60 years of age inclusive when signing the informed consent. For patients < 18 years of age, parent or legally authorized representative (LAR) should be willing and able to give informed consent. Non-English speaking patients are eligible for whom consent process will follow institutional guidelines.
- **3.1.6.** Patients with CNS disease are eligible.
- **3.1.7.** Patients must have adequate organ function and laboratory results (obtained within 14 days of enrollment):
  - **3.1.7.1.** Direct bilirubin  $\leq 2$  x upper limit of normal (ULN).
  - **3.1.7.2.** Serum creatinine  $\leq$  1.5 x ULN; or if serum creatinine > 1.5 x ULN, then serum creatinine clearance (CrCl)  $\geq$  50 mL/min (estimated by Cockcroft-Gault formula).
  - **3.1.7.3.** Alanine aminotransferase (ALT) and/or aspartate aminotransferase (AST)  $\leq$ 3 x ULN;  $\leq$ 5 x ULN in case of suspected leukemic liver involvement

Page | 9 04/25/2024

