# 5.3. Intrathecal Dosage and Administration.

Patients will receive intrathecal chemotherapy as per standard of care. Methotrexate, Cytarabine, hydrocortisone, or a combination of these is allowed on the study. The number of lumbar punctures with Intrathecal chemotherapies will depend on the age of the patient, clinical status, comorbidities, etc and will be determined by the PI.

**5.4.** Venetoclax is commercially available. Commercial supply of each will be used. Detail product information may be found in the product prescribing information and available through the following links:

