- 14. Lumbar puncture (T-ALL/T-LBL) for prophylactic intrathecal therapy: if prophylactic intrathecal therapy is foreseen by the treating physician, a lumbar puncture may be performed up to 3 days before the first dose of CB-103, and may be repeated at the discretion of the treating physician at the end of the first cycle and at the end of any subsequent cycles on or around day 28. If clinically feasible, one additional sample will be collected to determine the exposure of CB-103 in the CSF (this measurement will be done by a designated laboratory under Cellestia's responsibility).
- 15. For patients with PR or stable disease (SD) after the induction cycle(s) who may receive add-on selective therapy chosen by the investigator on the basis of the ongoing biomarker expression of the disease while continuing the treatment with the combination of CB-103 and venetoclax, the add-on therapy will be reported in details on the CRF.
- 16. EoT visit is to be done 5 days after the last dose of any study treatment, unless the patient starts any subsequent antitumor therapy (in which case the EoT visit should be performed before the start of the new therapy, whenever possible).
- 17 First follow-up visit will be 26 days after EoT (± 5 days), and every three months (± 14 days) thereafter, until EoS (i.e., death, patient's refusal, lost to follow-up) or study termination, whichever occurs first. Survival status and information on posterior antitumor therapies will be collected, telephone contact being acceptable.
- 18. If patient discontinued treatment without progression, tumor assessment will be done until progression or start of new antitumor treatment.
- 19. In case of relevant related toxicities (i.e., Grade>1), every 4 weeks until resolution or stabilization: information collected by telephone contact is acceptable.
- 20. Hepatitis B, C infection, and HIV will be obtained within 21 days of start of treatment.

Protocol 2021-0547 4/25/2024

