25/30     0.83 (0.66, 0.93)       26/30     0.87 (0.7, 0.95)       27/30     0.9 (0.74, 0.97)       28/30     0.93 (0.78, 0.99)       29/30     0.97 (0.82, 1)	23/30	0.77 (0.59, 0.88)
26/30     0.87 (0.7, 0.95)       27/30     0.9 (0.74, 0.97)       28/30     0.93 (0.78, 0.99)       29/30     0.97 (0.82, 1)	24/30	0.8 (0.62, 0.91)
27/30     0.9 (0.74, 0.97)       28/30     0.93 (0.78, 0.99)       29/30     0.97 (0.82, 1)	25/30	0.83 (0.66, 0.93)
28/30 0.93 (0.78, 0.99) 29/30 0.97 (0.82, 1)	26/30	0.87 (0.7, 0.95)
29/30 0.97 (0.82, 1)	27/30	0.9 (0.74, 0.97)
	28/30	0.93 (0.78, 0.99)
30/30 1 (0.87, 1)	29/30	0.97 (0.82, 1)
	30/30	1 (0.87, 1)

In secondary analysis, ORR will be summarized separately by Notch status as proportions with corresponding 95% Agresti-Coull confidence intervals. The difference in ORR between Notch groups will be assessed by Fisher's exact test.

Other measures of response (CR, Cri, PR, relapse, radiographic tumor response, CNS remission, CNS relapse) and minimal residual disease (MRD) will be summarized as proportions with corresponding 95% Agresti-Coull confidence intervals.

Duration of Response (DoR), Overall Survival (OS), and event-free Survival (EFS) will be summarized using Kaplan-Meier methods.

In exploratory analyses, correlations between ORR and pharmacokinetic and pharmacodynamics markers will be summarized. Rates of patients transitioning to Hematopoietic stem cell transplant (HSCT) will be summarized. Endpoints may be further summarized separately by Notch status.

Additional statistical methods may be used.

The Investigator is responsible for completing an efficacy/safety summary reports and submitting it to the IND Office Medical Affairs and Safety Group, for review and approval.

This should be submitted after the first 10 evaluable patients complete 1 cycle of study treatment, and every 10 evaluable patients, thereafter. Efficacy summary will be submitted for every 10 evaluable patients after they complete 2 cycles of therapy.

Page | 52 04/25/2024

A copy of the safety summary report should be placed in the Investigator's Regulatory Binder under "sponsor correspondence".

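### Section 7.1 ties intrathecal therapy to CNS disease found after enrolment, against 5.3, 3.2.13.4, 10.4.3 c) and calendar footnote 14, and CNS remission is anchored at diagnosis rather than at study entry

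*Combined protocol and SAP*

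**What the plan says.** **Intrathecal therapy.**
- Section 7.1: "Prophylactic or therapeutic intrathecal therapy is allowed, if central nervous system leukemia involvement is diagnosed after enrollment in this clinical trial".
- Section 5.3: "Patients will receive intrathecal chemotherapy as per standard of care". The number of lumbar punctures "will depend on the age of the patient, clinical status, comorbidities, etc and will be determined by the PI".
- Exclusion 3.2.13.4 lets prophylactic intrathecal chemotherapy be given until 1 day before the first CB-103 dose and sets no CNS condition.
- Section 10.4.3 c) names standard-of-care intrathecal treatment as part of the treatment plan and has the monitor check its timing against the protocol.
- Inclusion 3.1.6: "Patients with CNS disease are eligible".

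**Lumbar puncture.** Table 16 has a row for lumbar puncture and CSF sampling, marked at screening and near the end of each cycle. Its footnote 14 qualifies the row: "if prophylactic intrathecal therapy is foreseen by the treating physician, a lumbar puncture may be performed up to 3 days before the first dose", and it "may be repeated at the discretion of the treating physician at the end of the first cycle" and of later cycles.

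**CNS measures.** Section 9.1.4.1 defines CNS remission as reaching CNS-1 in a patient who was CNS-2 or CNS-3 at diagnosis. Section 9.1.4.2 defines CNS relapse as new CNS-3 status, clinical signs of CNS leukemia, or new CNS-2 status on two consecutive lumbar punctures. Section 12 lists "Other measures of response (CR, Cri, PR, relapse, radiographic tumor response, CNS remission, CNS relapse", together with MRD, to be reported as proportions with 95% Agresti-Coull intervals.

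**The concern.** Two things can go wrong if the text is followed literally.

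First, whether a patient may have intrathecal therapy depends on the section consulted. Section 7.1 attaches a condition that the other passages do not have, and the condition cannot be met by a patient whose CNS disease was known at entry. Intrathecal therapy bears directly on CNS remission and CNS relapse, so both measures would reflect which section was followed. The monitoring check in 10.4.3 c) would also have no single standard.

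Second, in a relapsed or refractory population, status at diagnosis can mean the original diagnosis. A patient whose CNS disease cleared on earlier treatment then meets the remission definition without any effect of the study drugs. Conversely, a patient who was CNS-1 originally but CNS-2 or CNS-3 at entry falls outside the definition.

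Discretionary lumbar puncture adds to this. Sampling follows the physician's plan to give prophylaxis, so who is tested is linked to who is treated.

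**Working it through.** **Step 1. The intrathecal passages side by side.**

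| Place | Content | CNS diagnosis required? | Covers CNS disease at entry? |
|---|---|---|---|
| 5.3 | Patients receive it as standard of care | No | Yes, by its general wording |
| 3.2.13.4 | Prophylaxis allowed shortly before first dose | No | Not addressed |
| Footnote 14 | Puncture when prophylaxis is planned | No | Not addressed |
| 10.4.3 c) | Part of the treatment plan | No | Not addressed separately |
| 7.1 | Allowed if CNS involvement is found after enrolment | Yes | No |

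Section 7.1 stands alone. Sections 5.3 and footnote 14 can be read together: both leave lumbar puncture to clinical judgement, though they name different decision-makers (the PI and the treating physician).

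**Step 2. The remission anchor.** The documents give no CNS rate, so the following is assumed for illustration. Let 3 patients be CNS-2/3 at entry, of whom 1 clears: 1/3 = 33%. Let 3 more have been CNS-2/3 at original diagnosis but CNS-1 at entry. Under the literal definition they count as remissions: (1 + 3)/(3 + 3) = 4/6 = 67%. The added responders owe nothing to study treatment.

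**Step 3. What a missing lumbar puncture does.** CNS remission needs a repeat CNS status, and the CNS-2 limb of relapse needs two punctures. Clinical signs alone can still establish a relapse. The documents do not define CNS-1, CNS-2 and CNS-3, so reading CNS-3 as a CSF result is an assumption.

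**Step 4. Sensitivity of the relapse proportion to the denominator.** Agresti-Coull: ñ = n + z², p̃ = (x + z²/2)/ñ, limits p̃ ± z√(p̃(1 − p̃)/ñ), with z = 1.96 and limits cut at 0 and 1.

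The plan's own Table 20 comes first. For 2/30: ñ = 33.84, p̃ = (2 + 1.92)/33.84 = 0.116, limits 0.008 and 0.224, which round to the stated (0.01, 0.22). All 31 rows of Table 20 reproduce to two decimals.

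Then assume 2 observed CNS relapses and vary the number evaluated:

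| Evaluated | Proportion | 95% interval |
|---|---|---|
| 30 | 6.7% | 0.8% to 22.4% |
| 20 | 10.0% | 1.6% to 31.3% |
| 15 | 13.3% | 2.5% to 39.1% |
| 10 | 20.0% | 4.6% to 52.1% |

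If 10 of 30 were not evaluated at all, the true share lies between 2/30 = 6.7% and (2 + 10)/30 = 40.0%. The upper figure is a bound, not an expectation, since clinical signs would reveal some relapses.

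**The case against.** The best defence is that 7.1 is one badly drafted sentence. It does not say only if. Read as an exclusive condition it defeats itself, because prophylaxis would require CNS disease already diagnosed. Four other passages permit or presuppose intrathecal therapy without the condition, and the prohibited list in 7.2 does not name it. This has force: the likely intent can be guessed. But a condition attached to a permission is naturally read as limiting it. Even if it governs therapeutic use alone, 7.1 still omits patients with CNS disease at entry.

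Stronger readings are tempting, and the documents do not support them:
- *Three incompatible rules.* Footnote 14 deals with lumbar puncture when prophylaxis is planned, not with who may be treated, and it fits with 5.3. The conflict is 7.1 against the rest.
- *CNS outcomes cannot be scored without a lumbar puncture.* Clinical signs alone meet the relapse definition, so relapse is at risk of under-detection rather than unscorable.
- *Untested patients are counted as not in remission.* Section 9.1.4.1 already limits remission to patients with CNS-2 or CNS-3 status. The gap is narrower: those known patients who have no repeat result.
- *The primary endpoint is affected.* CR and PR require absence of extramedullary disease, but the documents do not say that CNS disease counts there.

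It is also fair that every magnitude above is assumed, and that 6.7% to 13.3% lies within the plan's own interval for 2/30.

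**Conclusion.** The point holds in limited form. Section 7.1 contradicts 5.3, 3.2.13.4, footnote 14 and 10.4.3 c) on its natural reading, and on any reading it does not provide for patients who enter with CNS disease. The remission definition can credit a patient who is already CNS-1 at entry. This rests on taking diagnosis as the original diagnosis, which the text allows and does not exclude. With lumbar puncture discretionary, remission may be unassessable in some patients and relapse under-detected.

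The size cannot be derived from the documents, and the illustrations show sensitivity only. CNS remission and CNS relapse appear in no stated objective and are reported descriptively. As written, ORR and the BOP2 boundaries do not use them. The point is minor, but following the text literally would give wrong results, and the repair is cheap.

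**What to change.** 1. Reconcile 7.1 with 5.3, 3.2.13.4, footnote 14 and 10.4.3 c), so that one rule covers every eligible patient, including those with CNS disease at entry. Which clinical rule is right is for the investigators and is not proposed here.
2. Change 9.1.4.1 so that CNS remission starts from CNS-2 or CNS-3 status at study entry, and say openly that the definition has changed.
3. In Section 12, report CNS remission among all patients with CNS-2 or CNS-3 at entry, showing those without a repeat CSF result as not assessed. Add a sensitivity analysis limited to those assessed. The assessed group should not be the main denominator: the repeat puncture is at the physician's discretion, so that restriction would introduce selection.
4. Report CNS relapse with the number of patients who had a post-baseline CNS evaluation, clinical or CSF, alongside the intrathecal exposure that the CRF already captures.

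The cost is protocol and analysis wording, and somewhat wider intervals where fewer patients are evaluated. No new procedure is needed. Missing CSF results stay missing, but they become visible.

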# 8. Visit schedule and study assessments

Written ICF for participation in the study must be obtained from the patient, signed and dated before performing any study procedure. Patients will be informed about the study drug and will receive pertinent information regarding the study objectives, possible benefits, and potential AEs. They will also receive information on the follow-up procedures and possible risks they will be exposed to. The ICF also informs patients about how biological samples will be obtained and collected and its legal implications. Patients are allowed to enter the study based on confirmation of the eligibility criteria (refer to inclusion and exclusion criteria in **Section 3.1.** and **Section 3.2.**) at screening/baseline.

Assessments scheduled for days 1 of each cycle must be performed within 48 hours prior to study treatment administration, unless otherwise indicated in the schedule of assessments, in order to confirm to the patient if treatment can continue. All examinations listed below will be performed according to the Schedule of Assessments outlined in **Table 16**.

All screening tests and evaluations must be completed and reviewed to confirm that patients meet all eligibility criteria within 21 days prior to the first administration of study medication. Disease assessments, such as bone marrow samples (aspirate and/or biopsy), EKG and LVEF evaluation, such as ECHO/MUGA scan, available and performed as part of clinical practice prior to obtain the signature of the ICF, and within 21 days prior to treatment start, are accepted. Therefore, such evaluations are not required to be repeated during the screening period.

Patients should be admitted for Cycle 1 days 1-7 to monitor for any adverse events and for completion of study evaluations due on day 5. Patients may be discharged after the completion of study evaluations at the discretion of the treating physician if drug combination is being tolerated without need for close monitoring for adverse events and patient is clinically stable for safe discharge.

- **8.1. Medical History and Demographic Data**: Medical history includes clinically significant diseases, surgeries, reproductive status, smoking history, use of alcohol and drugs of abuse, all medications (e.g., prescription drugs, over the counter drugs, herbal or homeopathic remedies, nutritional supplements) and physical/occupational/exercise. Demographic data will include year of birth, sex and self reported race/ethnicity (collecting this information is essential in order to be able to evaluate the results of this study, for example, in the case of PK outliers or important between-patient differences in terms of treatment effect). Evaluation of the inclusion and exclusion criteria will be performed at the screening visit.
- **8.2. Disease History**: The patients' disease history from the time of diagnosis (including any biomarker information and details regarding anti-neoplastic treatments they have received in the past) will be collected at screening. The exact parameters to be collected will be outlined on the respective screening eCRF pages. Disease history will be taken at the screening visit.
- **8.3. ECOG performance status**: Performance status will be measured using the ECOG performance status scale (**Table 15a**). Patient's performance status should preferentially be assessed by the same person throughout the study.

**Table 15a**: ECOG performance status grading

Grade	Performance Status
0	Fully active, able to carry on all pre-disease performance without restriction
1	Restricted in physically strenuous activity but ambulatory and able to carry out workof a light or sedentary nature, i.e., light housework, office work
2	Ambulatory and capable of all self-care but unable to carry out any work activities. Upand about more than 50% of waking hours

Protocol 2021-0547 4/25/2024

3	Capable of only limited self-care, confined to bed or chair more than 50% of wakinghours
4	Completely disabled. Cannot carry on any self-care. Totally confined to bed or chair
5	Dead

Source: http://www.ecog.org/general/perf stat.html

Lansky scale may be used with adolescent of age  $\leq$  16 years (Table 14b). It is rated by parents based on their child's activity over the past week. Parents fill out the assessment based on the directions on the form, and the form is readministered over time to assess for changes in performance status.

Table 15b: Lansky performance status grading

Rating	Description
100	Fully active, normal
90	Minor restrictions with strenuous physical activity
80	Active, but gets tired more quickly
70	Both greater restriction of, and less time spent in, active play
60	Up and around, but minimal active play; keeps busy with quieter activities
50	Lying around much of the day, but gets dressed; no active play; participates in all quiet play and activities
40	Mostly in bed; participates in quiet activities
30	Stuck in bed; needs help even for quiet play
20	Often sleeping; play is entirely limited to very passive activities
10	Does not play nor get out of bed
0	unresponsive

**8.4. Vital signs and physical exam:** Oral body temperature, respiratory rate, sitting blood pressure, and sitting heart rate will be obtained while the patient is in a semi-supine/supine position after resting for approx. 5 minutes. Vital signs should be measured prior to blood draw or at least 10 minutes after the last blood draw. Additional determinations include body height (only at **Screening**) and body weight.

A complete physical examination should include an examination of head, eyes, ears, nose, and throat, as well as cardiovascular, dermatological, musculoskeletal, respiratory, gastrointestinal, genitourinary, and neurological systems. As part of the tumor assessment, physical exams should also include evaluation of presence and degree of increase of lymph nodes, hepatomegaly, and splenomegaly.

Eye examinations will be performed by an ophthalmologist during screening, at EOT, and in case of abnormalities at the safety follow-up visit. An extended eye examination including invasive ophthalmologic assessments should be performed by an ophthalmologist during the treatment period, in case significant abnormalities are experienced by the patient or seen by the study doctor at the regular eye evaluation as part of the physical examinations.

The following standard ophthalmological assessments performed by an ophthalmologist are recommended:

Page | 31 04/25/2024

- 1. Visual acuity test
- 2. Intraocular pressure test
- 3. Slit-lamp test
- 4. Dilated fundus test
- 5. Colour-vision (Ishihara-plate) test

Additional assessments or tests may be conducted by an ophthalmologist as clinically indicated. Invasive ophthalmologic assessments such as electroretinography (ERG) may be conducted if feasible, at the discretion of the site and may be conducted at the time when visual symptom(s) are reported (if any).

For any significant abnormalities seen at the eye examination, all assessed parameters and findings should be documented in the respective eCRF pages and source documents.

- **8.5. Pregnancy tests and assessment of fertility**: Only female patients of childbearing potential must undergo serum and urine pregnancy tests
- **8.6. Disease assessment**: Disease assessment by bone marrow samples (aspirate and/or biopsy), cytogenetics and flow cytometry is done at baseline screening and at completion of each treatment cycle. A bone marrow biopsy and/or aspirate will be obtained to assess bone marrow cellularity and to determine the percentage of leukemic blasts, including assessment of minimal residual disease (MRD) to confirm remission status.

At the baseline assessment, bone marrow biopsy and/or aspirate is within 3 weeks and no less than 1 day before the first drug dose. Then on each cycle, patients are assessed for disease response by bone marrow biopsy and/or aspirate on day 28. If the blasts in bone marrow are <5% but marrow is hypocellular (cellularity  $\leq$ 15%) on day 28 ( $\pm$ 3 days), then a repeat bone marrow biopsy and/or aspirate is obtained 1 week later to assess response; if residual leukemia is present, repeated bone marrow biopsy and/or aspirate will be obtained as medically indicated.

Only for patients with extramedullary disease or as clinically indicated a PET-CT will be performed at baseline and if positive, also at end of the induction and of the reinduction cycles, and thereafter as clinically indicated. A time window of  $\pm$  3 days is allowed for the tumor assessments. A wider time window is allowed only at baseline; however, assessments should be performed as close as possible to the 1st drug administration and if feasible, not later than 3 weeks prior to the 1st drug administration

